11.3 Severity Assessment

For all AEs occurring during the clinical trial, the Investigator is to classify and report the intensity of AEs using the following definitions as a guideline:

- Mild: awareness of signs and symptoms, but easily tolerated
- Moderate: discomfort, enough to cause interference with usual activity
- Severe: incapacitating, with inability to work or perform usual activity.

11.4 Causality Assessment

The Investigator is to assess the causal relationship (causality) between an adverse event and the investigational product and/or the clinical trial procedure according to the following definitions (Decision of 25 November 2013 on Guideline on Annex I to Regulation (EC) No 1223/2009 (2013/674/EU) – Causality assessment of undesirable effect caused by cosmetic products):

- Very likely
- Likely
- Unlikely
- Excluded

Medical judgment should be used to determine the relationship, considering all relevant factors including the pattern of reaction, temporal relationships, positive de-challenge or re-challenge, relevant medical history, and confounding factors such as co-medication or concurrent diseases.

Protocol GLI.04.US.SL.035

CONFIDENTIAL

11.5 Collection, Management and Reporting Procedures

The period of collection of adverse events starts from the time of signature of the Informed Consent Form (ICF) by the subject until the end of the subject's participation in the clinical study.

If a Serious Adverse Event (SAE) is on-going at the final clinical trial visit, it should be followed by the Investigator until it has resolved or has reached a stable condition.

After the subject completes the clinical study, the Investigator should also inform the Sponsor (see Sponsor's contact details below) if he/she becomes aware of an SAE involving a subject who has participated in the clinical study.

At each post enrollment visit, the Investigator will question the subject about AEs using an open non persuasive question to elicit reporting of AEs, for example "*Have you noticed any change in your health since the last visit?*" Direct questioning and examination will be performed when appropriate.

The Investigator will obtain and maintain in the subject's files all pertinent medical records, and (if applicable) information and medical judgment from colleagues who assisted in the treatment and follow-up of the subject. If necessary, the Investigator will contact the subject's personal physician or hospital staff to obtain further details.

As a minimum, Investigators are requested to report in the Case Report Form (CRF) and in the report all related adverse events (i.e., cosmetic adverse events) and all Serious Adverse Events, whether related or not.

11.5.1. Management and reporting procedures for cosmetic adverse events (i.e., related AEs)

Cosmetic adverse events should be recorded in the CRF and summarized in the report in a summary table with at minimum the subject number, AE number, AE diagnosis or signs and symptoms, location, date of onset, seriousness, severity, action taken, relationship, date of resolution and concomitant treatment associated as well as a detailed narrative of the event.

In addition, based on his/her medical judgment, the Investigator will assess whether an cosmetic adverse events requires immediate (i.e. within 24 hours) reporting to the Sponsor. In such cases, the summary table will be sent to the Sponsor, along with the AE narrative and any other relevant information (concomitant treatments, product weighing, ...).

All cosmetic adverse events should be appropriately documented, i.e. any relevant information such as demographics, medical history and concomitant therapies should be recorded in the CRF.

The Investigator is to monitor and record the progress of the adverse effect until the last subject's study visit.

The Investigator is to update the AE narrative as appropriate, each time follow-up information is collected and when the final outcome of the adverse effect is known.

Protocol Version 02: 29 January 2024

This document contains confidential, proprietary information.

Protocol GLI.04.US.SL.035

CONFIDENTIAL

11.5.2. Management and reporting procedures for Serious Adverse Events

The Investigator is to take the following steps:

1. Take prompt and appropriate medical action, if necessary. The safety of clinical trial subjects is the first priority.
2. Ensure the AE is classified as an SAE. Immediately inform the Sponsor's representative of the event by email (see both contact details below) and discuss further actions to be taken:

Global Vigilance email: [contact]

US Vigilance email: [contact]

3. Complete the Serious Adverse Event (SAE) form provided by the Sponsor's representative **Within 24 hours**, send by e-mail **to the Sponsor's representative** the completed SAE form, accompanied any other relevant information (e.g., test results or medical records).
4. Monitor, record and send to Sponsor's representative the progress of the event until it resolves or reaches a stable outcome, with or without sequelae (send the updated SAE form with follow-up information and any other relevant information to Sponsor's representative).
5. Obtain and maintain in the subject's file all pertinent medical records, information, and medical judgments from colleagues who assisted in the treatment and follow-up of the subject. If necessary, contact the subject's personal physician or hospital staff to obtain further details.
6. If applicable, comply with the regulatory requirement(s) related to the reporting of SAEs to the Institutional Review Board (IRB) / Independent Ethics Committee (IEC).

11.6 Pregnancy

Pregnancy itself is not to be considered as an adverse event. If a pregnancy occurs during the clinical trial, **the product application should be stopped immediately**, the subject should be withdrawn from the clinical study and Sponsor's representative (see Sponsor's contact details above) should be informed **within 24 hours**.

Pregnancy must be recorded as a reason for discontinuation in the exit form of the CRF.

No specific follow-up of pregnancy is required, except if it is a regulatory requirement in the country(ies) where the clinical trial is conducted.

Protocol GLI.04.US.SL.035

CONFIDENTIAL

12. STATISTICAL ANALYSIS

12.1 General

All study data will be listed in subject data listings.

All continuous endpoints will be summarized descriptively including N, mean, median, standard deviation, minimum and maximum values, for the observed value as well as the change from Baseline. Categorical endpoints will be presented in frequency tables with number and percentage of observations for each level.

Confidence intervals will be two-sided and constructed at a confidence level of 95%. Statistical tests will be performed at a significance level of 5%, and *p* values will be two-sided.

12.2 Analysis Population

The following populations will be defined:

Intention-to-treat (ITT)	Includes all subjects who receive the test products, i.e., at least one follow-up visit completion. Subjects are analyzed based on the as treated principle.
Per protocol (PP)	Includes all subjects in ITT who complete the study without any deviations that are considered to have substantial impact on the primary effectiveness outcome.

ITT is the primary population for all efficacy and safety analyses. The primary efficacy analysis will be repeated using the PP analysis set if there is at least a 10% difference in the number of subjects between the PP and ITT sets.

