9. STUDY PROCEDURES

There will be 4 visits during the course of the study as illustrated in Table 1:

1. Visit 1 – Day 0 (screening/baseline)
2. Visit 2 – Week 2 (follow-up)
3. Visit 3 – Week 4 (follow-up)
4. Visit 4 – Week 8 (end of study or EOS)

Table 1. Study Visit and Assessments

Procedure	Visit 1	Visit 2	Visit 3	Visit 4
	D0	2 weeks after Baseline (± 3 days)	4 weeks after Baseline (± 5 days)	8 weeks after Baseline (± 5 days)
	Screening / Baseline	Follow-up	Follow-up	EOS
Informed consent	X			
Demographic	X			
Inclusion and exclusion criteria	X			
Concomitant medications	X	X	X	X
Lesion photography 
 Digital photography Macroscopic imaging¹ Capacitance imaging¹ 	X	X	X	X
Investigator clinical grading	X	X	X	X
Subjective tolerability assessment	X	X	X	X
Quality of Life questionnaire	X			X
Self-assessment questionnaire		X	X	X
Adverse events reporting		X	X	X
Study products	W/D	I/W	I/W	I/W/C
Subject diaries	D	C/R/D	C/R/D	C/R

For study products and daily diaries: D=Distribute, C=Collect, R=Review, W=Weigh, and I=Inspect (visually).

¹Performed at Site 2 only (n = 20-25).

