9.2 Discontinued Subjects

Any subject is free to discontinue his/her participation in this study at any time and for whatever reason, specified or unspecified, and without prejudice.

An Investigator may decide to discontinue a subject from the study for safety reasons or when it is in the best interest of the subject. Galderma Laboratories, L.P. may also decide to prematurely terminate or suspend the study or the participation of a subject in the study. All data gathered on the subject prior to termination should be made available to Galderma Laboratories, L.P.

Criteria for the discontinuation of a subject during the study will include the following:

- Adverse Event
- Lack of Effect
- Pregnancy
- Subject Request
- Protocol Violation
- Lost to Follow-up
- Any unmanageable factor, in the Investigator's opinion, that may significantly interfere with the protocol or interpretation of results.

Protocol Version 02: 29 January 2024

This document contains confidential, proprietary information.

Protocol GLI.04.US.SL.035

CONFIDENTIAL

The reason and date for withdrawal should be documented in the subject's source documents and CRFs. When possible, an explanatory comment should be added to further explain the reason for the withdrawal. If withdrawal of a subject occurs during a regular study visit, the CRF for that specific visit shall be completed as far as possible.

If a subject is withdrawn from the study, all data collected until the time of withdrawal will be used in the analyses. Subjects who receive study products and are withdrawn or discontinued from the study will not be replaced. For AEs still ongoing at the time of withdrawal, see Section 11.

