11.1 Tolerability Assessment

Tolerability assessment will be performed by the Investigator (dryness) and by subjects (burning/stinging and itching) using a 4-point analog scale (with half-point scores used as necessary to better describe the clinical condition). Investigator and subjects will grade the degree of irritation of target lesion areas, at Baseline, Week 2, 4, and 8.

Table 4. Tolerability Scales

Score	Grade	Description
Itching: as reported by the subject within the last 24 hours		
0	None	No itching
1	Mild	Slight itching, not really bothersome
2	Moderate	Definite itching that is somewhat bothersome
3	Severe	Intense itching that may interrupt daily activities and/or sleep
Dryness: as assessed by the investigator		
0	None	No dryness
1	Mild	Slight, but definite roughness
2	Moderate	Definite roughness
3	Severe	Marked roughness
Burning/Stinging: as reported by the subject within the last 24 hours		
0	None	No burning
1	Mild	Slight burning sensation; not really bothersome
2	Moderate	Definite warm, burning that is somewhat bothersome
3	Severe	Hot burning sensation that causes definite discomfort and may interrupt daily activities and/or sleep

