12.4 Statistical Analysis Plan

Mean of the change from Baseline will be estimated at applicable post-Baseline timepoint. The null hypothesis, that the mean change from Baseline is zero, will be tested using methods described in

Table 5.

The following will be calculated and reported for each parameter at applicable post-Baseline timepoint(s):

$$\text{Percent mean change from baseline} = \frac{(\text{visit mean score} - \text{baseline mean score})}{\text{baseline mean score}} \times 100$$

$$\text{Percent of subjects improved/worsened} = \frac{(\text{number of subjects improved/worsened from baseline})}{\text{total number of subjects}} \times 100$$

Protocol Version 02: 29 January 2024

This document contains confidential, proprietary information.

Protocol GLI.04.US.SL.035

CONFIDENTIAL

Table 5. Statistical Analysis Plan

Evaluation	Change from Baseline	Notes/Interpretation
Clinical Grading 
 BSA TLSS PGA 	One-sample t-test; If normality fails, a Wilcoxon signed-rank test will be used.	A decrease in scores indicates an improvement.
Tolerability Grading 
 Dryness Burning/Stinging Itching 	One-sample t-test; If normality fails, a Wilcoxon signed-rank test will be used.	A decrease in scores or lack of significant increase indicates tolerability/safety of the treatment products.
Macroscopic Imaging 
 Skin smoothness Skin roughness 	One-sample t-test; If normality fails, a Wilcoxon signed-rank test will be used.	A decrease in values indicates an improvement in skin smoothness. An increase in values indicates an improvement in roughness.
Capacitance Imaging 
 Homogeneity 	One-sample t-test; If normality fails, a Wilcoxon signed-rank test will be used.	An increase in values indicates a homogeneous moisture distribution.
QoL Questionnaire	Wilcoxon signed-rank test	A decrease in response values indicates an improvement.
Self-Assessment Questionnaire	N/A	Percentage of favorable and unfavorable responses will be provided for each question.

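### The only set named for safety analyses requires a completed follow-up visit, so exposed subjects who leave before completing Visit 2 fall outside every ITT-based safety summary.

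*Combined protocol and SAP*

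**What the plan says.** Section 12.2 defines two sets.

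- **ITT:** "Includes all subjects who receive the test products, i.e., at least one follow-up visit completion".
- **Per protocol:** "Includes all subjects in ITT who complete the study" without deviations of substantial impact. It is a subset of ITT.

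The section then states: "ITT is the primary population for all efficacy and safety analyses". No separate safety set is defined.

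Section 9.2 says that when a subject is withdrawn, "all data collected until the time of withdrawal will be used in the analyses". Section 11.5 collects adverse events from signature of the consent form to the end of participation.

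In Section 9, Table 1, the first follow-up is Visit 2 at Week 2 (± 3 days), and no early-termination visit is scheduled. For tolerability, Section 11.1 says: "Investigator and subjects will grade the degree of irritation of target lesion areas, at Baseline, Week 2, 4, and 8". Table 5 in Section 12.4 gives the reading of those scores: "A decrease in scores or lack of significant increase indicates tolerability/safety of the treatment products".

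**The concern.** Receiving product and completing a follow-up visit are different conditions, yet the definition treats the second as a restatement of the first. Read literally, membership of the safety set depends on something that happens after exposure and that the products can themselves cause. Section 9.2 lists an adverse event among the reasons for discontinuation.

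Tolerability is half of the primary objective in Section 4.1, and Table 5 counts the absence of a significant increase as evidence of it. Leaving out subjects who went home with irritation therefore pushes the result in the direction the study hopes to show. Two statisticians, one following Section 9.2 and the other Section 12.2, could also report different AE percentages from the same data.

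**Working it through.** **Who is outside the set.** The plan states no figure on this point, so the first step is to follow individual cases through the text.

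1. A subject receives product, stops using it in the first week and attends Visit 2. A follow-up visit has been completed, so the subject is in ITT.
2. A subject receives product, misses Visit 2 and attends Visit 3. The subject is in ITT.
3. A subject receives product and leaves the study before completing Visit 2. The subject meets the first clause of the ITT definition but fails the second. Per protocol is a subset of ITT, so the subject is in no defined set. Section 9.2 nevertheless says the subject's data will be used.

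Only case 3 is affected.

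**What happens to a case 3 subject's data.**

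- *Adverse events.* Section 11.2.2 records irritation as a related AE if it permanently stops application or leads to a prescribed corrective treatment other than a moisturizer or emollient. Section 11.5.1 puts related AEs in a summary table with a narrative, and Section 12.1 lists all study data. None of these sets a visit condition. The event is therefore disclosed, but no all-exposed denominator is defined for a rate.
- *Tolerability scores.* Grading takes place at Baseline and Weeks 2, 4 and 8. A case 3 subject has no post-baseline score, so no change from Baseline can be computed whichever set is used.
- *Percent worsened (Section 12.4).* The formula divides by the total number of subjects without saying which set supplies that total.

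**Size, under stated assumptions.** The documents give no dropout rate and no AE rate. Assume k case 3 subjects, each with one related AE, and no related AE among the ITT subjects. Take the ITT size as 40 or 50, the planned range of completers in Section 6.1. The ITT proportion is 0/n and the all-exposed proportion is k/(n + k).

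Intervals are exact two-sided 95% (Clopper-Pearson). For x events in N, the lower limit is the 0.025 quantile of Beta(x, N − x + 1) and the upper limit is the 0.975 quantile of Beta(x + 1, N − x). With x = 0 the lower limit is 0 and the upper is 1 − 0.025^(1/N), which for N = 40 is 8.8%.

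| k | ITT, n = 40 | All exposed | ITT, n = 50 | All exposed |
|---|---|---|---|---|
| 1 | 0/40, upper 8.8% | 1/41 = 2.4%, upper 12.9% | 0/50, upper 7.1% | 1/51 = 2.0%, upper 10.4% |
| 3 | 0/40, upper 8.8% | 3/43 = 7.0%, upper 19.1% | 0/50, upper 7.1% | 3/53 = 5.7%, upper 15.7% |
| 5 | 0/40, upper 8.8% | 5/45 = 11.1%, upper 24.1% | 0/50, upper 7.1% | 5/55 = 9.1%, upper 20.0% |

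If two of 40 ITT subjects also had a related AE, ITT would show 2/40 = 5.0%. The all-exposed figures would be 3/41 = 7.3%, 5/43 = 11.6% and 7/45 = 15.6%.

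**Chance that the case arises at all.** With an assumed probability p of leaving before completing Visit 2, the chance of at least one such subject among N exposed is 1 − (1 − p)^N.

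| p | N = 40 | N = 50 |
|---|---|---|
| 2% | 55.4% | 63.6% |
| 5% | 87.1% | 92.3% |
| 10% | 98.5% | 99.5% |

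**The case against.** The best defence is that the plan already has an inclusive reading. The first clause of the ITT definition and Section 9.2 both point to all exposed subjects, and the related AEs are tabulated and narrated whatever set is used. On that view the second clause is loose drafting. It stands that the events are disclosed. It does not cure the definition, because listings and narratives supply no rate and the set named for safety analyses still carries the visit condition.

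Four stronger readings are tempting, and the documents do not support them.

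- *A reader might infer that anyone who stops the products before Week 2 is dropped.* The condition is a completed visit, not continued use.
- *A reader might infer that early irritation disappears from the safety results.* Sections 11.2.2, 11.5, 11.5.1 and 12.1 keep related AEs in the report.
- *A reader might infer that a safety set would change the tolerability-score tests.* It would not, because no score is scheduled between Baseline and Week 2.
- *A reader might infer that the ITT interval would exclude the all-exposed rate.* With 40 in ITT, one or three such subjects give 2.4% or 7.0%, both inside 0 to 8.8%. Among the cases shown, only five takes the rate outside.

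It is also fair to say that Table 5 has no AE row, so 0/40 illustrates an ITT-based summary and is not a planned output. The documents give no timing for intolerance, and Section 6.4 excludes subjects with known hypersensitivity to cosmetics or personal care products.

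**Conclusion.** The point holds in this form. The only set named for safety requires a completed follow-up visit, which contradicts its own first clause and Section 9.2. Exposed subjects who leave before completing Visit 2 are outside both numerator and denominator of every ITT-based safety summary. Where such a subject leaves with a related AE, the omission lowers the ITT rate.

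The inconsistency is certain from the text. The size is not, because it rests entirely on an assumed number of early leavers and on each having a related AE. Over 1 to 5 such subjects, with 40 others free of events, a reported 0% would be 2.4% to 11.1% of those exposed. Subjects who leave early without any event would move the rate slightly the other way. The loss concerns rates and denominators, not disclosure of the events.

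**What to change.** 1. In Section 12.2, add a safety set: all subjects who received product and applied it at least once, or whose use is unknown, regardless of follow-up. Use it for adverse events and discontinuations.
2. Report discontinuation for local intolerance as a count and percentage of all exposed subjects, beside the tolerability-score tables. This is needed because those tables cannot contain a score from before Week 2. Counting such subjects as worsened within the score tables would be a composite rule open to debate, and the correction does not need it.
3. Rename the current set as a full analysis set (at least one follow-up). Keep it for efficacy and change-from-baseline scores, and state how many exposed subjects it omits.
4. Say which set supplies the denominator of the percent improved or worsened in Section 12.4.
5. Reconcile Section 12.2 with Section 9.2 so that the use of data up to withdrawal has one meaning.

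The cost is wording and one extra denominator. Stated tolerability may look less favourable. No visit, procedure or sample size changes.

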12.3 Demographics and Subject Characteristics

Demographic endpoints and subject characteristics will be presented based on the ITT analysis set using descriptive statistics, as appropriate.

12.4 Statistical Analysis Plan

Mean of the change from Baseline will be estimated at applicable post-Baseline timepoint. The null hypothesis, that the mean change from Baseline is zero, will be tested using methods described in

Table 5.

The following will be calculated and reported for each parameter at applicable post-Baseline timepoint(s):

$$\text{Percent mean change from baseline} = \frac{(\text{visit mean score} - \text{baseline mean score})}{\text{baseline mean score}} \times 100$$

$$\text{Percent of subjects improved/worsened} = \frac{(\text{number of subjects improved/worsened from baseline})}{\text{total number of subjects}} \times 100$$

Protocol Version 02: 29 January 2024

This document contains confidential, proprietary information.

Protocol GLI.04.US.SL.035

CONFIDENTIAL

Table 5. Statistical Analysis Plan

Evaluation	Change from Baseline	Notes/Interpretation
Clinical Grading 
 BSA TLSS PGA 	One-sample t-test; If normality fails, a Wilcoxon signed-rank test will be used.	A decrease in scores indicates an improvement.
Tolerability Grading 
 Dryness Burning/Stinging Itching 	One-sample t-test; If normality fails, a Wilcoxon signed-rank test will be used.	A decrease in scores or lack of significant increase indicates tolerability/safety of the treatment products.
Macroscopic Imaging 
 Skin smoothness Skin roughness 	One-sample t-test; If normality fails, a Wilcoxon signed-rank test will be used.	A decrease in values indicates an improvement in skin smoothness. An increase in values indicates an improvement in roughness.
Capacitance Imaging 
 Homogeneity 	One-sample t-test; If normality fails, a Wilcoxon signed-rank test will be used.	An increase in values indicates a homogeneous moisture distribution.
QoL Questionnaire	Wilcoxon signed-rank test	A decrease in response values indicates an improvement.
Self-Assessment Questionnaire	N/A	Percentage of favorable and unfavorable responses will be provided for each question.

Questionnaires will be tabulated; and the frequency and percentage of all response options will be reported for each question and time point. For questionnaire inquiries without baseline response data, a binomial (sign) test will be performed to test if the proportion of the combined designated favorable responses is equal to the combined designated unfavorable responses for each applicable question. A higher percentage of favorable responses with a significant *p* value indicates positive subject perceptions of the study treatment.

A more appropriate analysis may be performed, which will be recorded in biostatistics note to file and/or in the study report.

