6. SELECTION AND DISPOSITION OF STUDY POPULATION

6.1 Number of Subjects

An appropriate number of subjects meeting inclusion/exclusion criteria listed below will be enrolled on the study to achieve minimum 40 (maximum 50 subjects) who complete the study as planned.

Each study site is to enroll and complete with 20-25 subjects, with 40-50 subjects expected to complete when combined.

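### The Week 8 analysis is observed-case with no missing-data method, although lack of effect is a listed reason to discontinue, and the percent formulas do not say which subjects they cover

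*Combined protocol and SAP*

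**What the plan says.** Section 12.4 estimates the mean change from Baseline at each post-Baseline visit. Table 5 tests it against zero with a one-sample t-test, or a Wilcoxon signed-rank test if normality fails. The same section says "The following will be calculated and reported for each parameter at applicable post-Baseline timepoint(s" and gives two formulas:

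- Percent mean change is the "visit mean score" minus the baseline mean, divided by the baseline mean.
- Percent improved or worsened is a count divided by the "total number of subjects".

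Neither formula says which subjects enter.

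Section 12.2 makes ITT primary for efficacy and safety and ties membership to "at least one follow-up visit completion". The per-protocol set requires completion. It is analysed only for primary efficacy, and only if it differs from ITT by at least 10% in number.

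Section 9.2 lists "Lack of Effect" and adverse events among the discontinuation criteria. Data up to withdrawal are used, and treated subjects who leave are not replaced. Section 6.1 sets the target as "minimum 40 (maximum 50 subjects) who complete the study as planned". It gives neither a number to enrol nor a dropout rate. Section 14.4 mentions missing data only as a data-entry matter.

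**The concern.** A one-sample test on change needs a value at Baseline and a value at the visit. Section 9.2 keeps a withdrawn subject's Week 2 and Week 4 values, but these cannot enter the Week 8 test as planned. If the subjects who leave are those who did not improve, or who were irritated, the Week 8 mean describes a more favourable group than the one that started. The per-protocol repeat does not probe this, because it removes non-completers as well.

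Tolerability has the same gap. Table 5 takes the absence of a significant increase as support for tolerability, so losing the worst cases would help that claim.

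The percent formulas add a second ambiguity. If the baseline mean comes from all ITT subjects and the visit mean from attendees, the percent change need not agree with the paired test reported beside it. Section 12.4 ends by allowing a more appropriate analysis, recorded in a note to file or in the report, so these choices could be made after the data are seen.

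**Working it through.** The plan states no effect size, SD, dropout rate or power, so there is no figure of its own to reproduce. Its only arithmetic, 2 sites × 20 to 25 = 40 to 50 completers, agrees.

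**Assumed inputs (not from the plan).** 40 completers with baseline TLSS 12 and change -3. Then 2, 5 or 10 ITT subjects who leave before Week 8, that is 2/42 = 4.8%, 5/45 = 11.1% or 10/50 = 20%. Their baseline is 9, 12 or 15. Among completers, 28 improved and 4 worsened.

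**1. Mean change at Week 8.** Observed-case: -3.00. Over all ITT subjects: (40 × -3 + d × c)/(40 + d), with d dropouts whose change is c.

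| Dropouts | Observed-case | c = 0 | c = +2 |
|---|---|---|---|
| 2 | -3.00 | -120/42 = -2.86 | -116/42 = -2.76 |
| 5 | -3.00 | -120/45 = -2.67 | -110/45 = -2.44 |
| 10 | -3.00 | -120/50 = -2.40 | -100/50 = -2.00 |

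With c = 0 the observed-case figure is larger by the ratio (40 + d)/40: 5%, 12.5% or 25%.

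**2. Percent mean change.** With the same subjects in both means, the result is -3/12 = -25.0%. The difference of the means then equals the mean paired change exactly. With mixed sets, the baseline mean is (40 × 12 + d × b)/(40 + d), where b is the dropouts' baseline, and the visit mean is 9.

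| Dropouts | b = 9 | b = 12 | b = 15 |
|---|---|---|---|
| 2 | -24.1% | -25.0% | -25.9% |
| 5 | -22.9% | -25.0% | -27.0% |
| 10 | -21.1% | -25.0% | -28.6% |

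For example, with d = 5 and b = 15, the baseline mean is 555/45 = 12.33 and (9 - 12.33)/12.33 = -27.0%. Mixing inflates the figure only when dropouts started worse, and shrinks it when they started better.

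**3. Percent improved and worsened.**

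| Dropouts | Improved, assessed | Improved, all ITT | Worsened, assessed | Worsened, all ITT | All dropouts counted as worsened |
|---|---|---|---|---|---|
| 2 | 28/40 = 70.0% | 28/42 = 66.7% | 4/40 = 10.0% | 4/42 = 9.5% | 6/42 = 14.3% |
| 5 | 70.0% | 28/45 = 62.2% | 10.0% | 4/45 = 8.9% | 9/45 = 20.0% |
| 10 | 70.0% | 28/50 = 56.0% | 10.0% | 4/50 = 8.0% | 14/50 = 28.0% |

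An all-ITT denominator lowers both rates. The last column is an upper bound, because it treats every dropout as worsened.

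**The case against.** The strongest reply is that undefined wording is not bias. Section 12.4 permits mixed sets but does not prescribe them, and on subjects with both values the percent change matches the paired test. The tests themselves are paired and cannot mix sets. Section 12.1 requires N for each summary, so attrition would show. All of this stands.

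A reader might infer that poor responders leave by rule. Section 9.2 gives no threshold and does not instruct sites to remove non-responders. It lists lack of effect as one possible reason. Dropouts with a follow-up visit also contribute at the visits they attended.

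A reader might also infer that dividing by all subjects only hides worsening. It lowers percent improved too, which is conservative for efficacy. Nor can the denominator literally mean the whole study for every parameter, since imaging is done at Site 2 only.

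Intolerance withdrawals are not invisible either. Section 11.2.2 records a local sign that permanently stops the product as a related adverse event, and Section 11.5.1 asks for a narrative.

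None of this supplies a missing-data method for Week 8 or a sensitivity analysis that tests the influence of those who left.

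**Conclusion.** The point holds as a gap in method and definition. As written, Week 8 is observed-case, some listed withdrawal reasons relate to outcome, and the only second analysis drops non-completers. Bias toward improvement is plausible if dropouts respond worse than those who stay. With 2 to 10 no-change dropouts beside 40 completers, a change of -3.00 becomes -2.86 to -2.40. Those inputs are assumed, and the true size cannot be derived from the documents.

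The documents do not support the stronger conclusion that efficacy is biased upward and worsening downward by the plan's own rules. The direction of any error in percent mean change depends on the dropouts' baseline scores, and the effect on percent improved and worsened depends on an unstated denominator. This is a cheap and worthwhile improvement, and not a flaw that invalidates the study.

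**What to change.** Amend Section 12.4 as follows.

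- **Main estimate.** For BSA, TLSS, PGA and the tolerability scores, estimate change at Weeks 2, 4 and 8 with one repeated-measures mixed model (visit as factor, baseline as covariate) on all post-baseline ITT values. Keep the planned t-test or Wilcoxon test as a supporting analysis.
- **Sensitivity.** Add one analysis that sets change to zero (baseline carried forward) for withdrawals due to lack of effect or an adverse event. QoL is measured only at Baseline and Week 8, so it needs this analysis alone.
- **Percent mean change.** Divide the mean paired change by the baseline mean of the same subjects.
- **Percent improved or worsened.** Report it over subjects assessed at that visit. As a separate sensitivity result, report it over all ITT subjects, with intolerance withdrawals counted as worsened in both numerator and denominator. Zero change is not a worst case for tolerability, so this second result is needed. Use a Site 2 denominator for imaging.
- **Reporting.** Give N per visit and withdrawals by reason. Include subjects who leave before any follow-up visit, because they fall outside ITT and the model cannot recover them.

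The cost is SAP wording and modest extra programming, with no new data. Some figures may become slightly less favourable.
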